**The following documents are currently attached to this item:**

*There are no documents attached for this item.*

## **Data confidentiality**

- Paper-based records will be kept in a secure location and only be accessible to personnel involved in the study.**
- Computer-based files will only be made available to personnel involved in the study through the use of access privileges and passwords.**
- Prior to access to any study-related information, personnel will be required to sign statements agreeing to protect the security and confidentiality of identifiable information.**
- Wherever feasible, identifiers will be removed from study-related information.**

A Certificate of Confidentiality will be obtained, because the research could place the subject at risk of criminal or civil liability or cause damage to the subject's financial standing, employability, or liability.

A waiver of documentation of consent is being requested, because the only link between the subject and the study would be the consent document and the primary risk is a breach of confidentiality. (This is not an option for FDA-regulated research.)
- Precautions are in place to ensure the data is secure by using passwords and encryption, because the research involves web-based surveys.**

Audio and/or video recordings will be transcribed and then destroyed to eliminate audible identification of subjects.

## **Subject Confidentiality**

Paper-based records will be kept in a secure location and only be accessible to personnel involved in the study. Electronic files will only be made available to personnel involved in the study through the use of access privileges and passwords. Prior to access to any study-related information, personnel will be required to sign statements agreeing to protect the security and confidentiality of identifiable information. Whenever feasible, identifiers will be removed from study-related information. Precautions are in place to ensure the data is secure by using passwords and encryption, because the research involves web-based surveys. The GUIDE App uses phone numbers and emails for account creation. They are secured by Okta and stored separately from app data. This data is later de-identified for analysis, and participants may delete their account after the study has ended.

## **Sensitive Research Information\***

Does this research involve collection of sensitive information about the subjects that should be excluded from the electronic medical record? [NOTE: This does not apply to: 1) research information that would not normally be included in the electronic medical record or 2) information that is in the electronic medical record as part of clinical care.]

No

## **Subject Privacy**

Privacy refers to the person's desire to control access of others to themselves. Privacy concerns people, whereas confidentiality concerns data. Describe the strategies to protect privacy giving consideration to the following: The degree to which privacy can be expected in the proposed research and the safeguards that will be put into place to respect those boundaries. The methods used to identify and contact potential participants. The settings in which an individual will be interacting with an investigator. The privacy guidelines developed by relevant professions, professional associations and scholarly disciplines (e.g., psychiatry, genetic counseling, oral history, anthropology, psychology).

Data from the study will only be shared with personnel that work on the study. Data from the GUIDE App will only be seen by the research team and the GUIDE App development team. Professional conduct will be expected by each member of the research team and advised to the GUIDE App team, and will be overseen by the PI, [name], in accordance with the privacy guidelines developed by the discipline of psychology.

## **Disclosures**

Will any data or specimens from Penn participants OR other research generated work product (e.g., intellectual property) be disclosed to any individuals, entities, or vendors, etc. outside of Penn?

No

**Data Protection\***

- Name**
- Street address, city, county, precinct, zip code, and equivalent geocodes**
  - All elements of dates (except year) for dates directly related to an individual and all ages over 89**
- Telephone and fax number**
- Electronic mail addresses**
- Social security numbers**
  - Medical record numbers**
  - Health plan ID numbers**
  - Account numbers**
  - Certificate/license numbers**
  - Vehicle identifiers and serial numbers, including license plate numbers**
  - Device identifiers/serial numbers**
  - Web addresses (URLs)**
  - Internet IP addresses**
  - Biometric identifiers, incl. finger and voice prints**
  - Full face photographic images and any comparable images**
  - Any other unique identifying number, characteristic, or code**
- None**

Does your research request both a waiver of HIPAA authorization for collection of patient information and involve providing Protected Health Information ("PHI") that is classified as a "limited data set" (city/town/state/zip code, dates except year, ages less than 90 or aggregate report for over 90) to a recipient outside of the University of Pennsylvania covered entity?

No

**Tissue Specimens Obtained as Part of Research\***

Are Tissue Specimens being obtained for research?

No

**Tissue Specimens - Collected during regular care\***

Will tissue specimens be collected during regular clinical care (for treatment or diagnosis)?

No

**Tissue Specimens - otherwise discarded\***

Would specimens otherwise be discarded?

No

**Tissue Specimens - publicly available\***

Will tissue specimens be publicly available?

No

**Tissue Specimens - Collected as part of research protocol\***

Will tissue specimens be collected as part of the research protocol?

No

**Tissue Specimens - Banking of blood, tissue etc. for future use\***

Does research involve banking of blood, tissue, etc. for future use?

No

**Genetic testing**

If genetic testing is involved, describe the nature of the tests, including if the testing is predictive or exploratory in nature. If predictive, please describe plan for disclosing results to subjects and provision

of genetic counseling. Describe how subject confidentiality will be protected Note: If no genetic testing is to be obtained, write: "Not applicable."  
Not applicable.

## Consent

### 1. Consent Process

#### Overview

Once participants are recruited and communication is established, interested invitees will be prompted to complete a brief screener on REDCap to determine eligibility based on inclusion criteria. After eligibility is established, they will be directed to review the Informed Consent Form and HIPAA Authorization Form via REDCap. These consent forms include a description of the study and expected roles and responsibilities of the participant, risks and benefits to participants, and confidentiality procedures (see attached). The consent forms also clearly state that participation in the study is completely voluntary, and participants can drop out of the study without penalty at any time. All consent forms follow the guidelines outlined by the University of Pennsylvania, and ethical guidelines set forth by the state and federal governments. Documentation of subject consent will be stored in a locked file in the PI or designees office at each study site or in one of the HIPAA-compliant servers described above.

#### Children and Adolescents

Not applicable.

#### Adult Subjects Not Competent to Give Consent

Yes. Not applicable.

### 2. Waiver of Consent

#### Waiver or Alteration of Informed Consent\*

No Waiver Requested

#### Minimal Risk\*

#### Impact on Subject Rights and Welfare\*

#### Waiver Essential to Research\*

#### Additional Information to Subjects

#### Written Statement of Research\*

No

#### If no written statement will be provided, please provide justification

#### The following documents are currently attached to this item:

*There are no documents attached for this item.*

## Risk / Benefit

#### Potential Study Risks

We do not anticipate any significant risks of participation. Possible risks for participants include experiencing discomfort in talking about their experiences and emotions during the post-trial interview or in filling out the surveys. There is a chance that participants with suicidal ideation join the trial, given the higher risk of suicide among veterans, soldiers and first responders. In the event that a participant is

in imminent danger to themselves or others, PI [name], a psychologist, will remain on-call to address all participant related risk concerns for the duration of the study. Our provisions for clinical management regarding suicide risk in participants include: 1) Flagging of any suicidal intentions, thoughts, or behaviors disclosed in the GUIDE App to the research team within 24 hours (via GUIDE moderators); 2) Offering the participants immediate access to mental health resources via the SOS button in the GUIDE app, including the 988 Suicide and Crisis Lifeline; 3) Reviewing the flagged message with PI [name] within 12 hours of receipt of the escalation; 4) If PI [name] determines that the message is indeed deemed to be indicative of suicidal risk, she will contact the participant within 12 hours by phone and/or email to ensure they are connected to the appropriate resources. PI [name] will contact a local hospital if indicated (because the study will be conducted remotely, each participant is likely to be proximal to a different hospital or emergency room). In order to maintain sufficient safety and risk monitoring (including the ability to contact the participant directly in the case of potential imminent clinical risk), we must have access to personally-identifiable information (i.e., phone number, email address, and alternate contact information for the participant).

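### No faster staff route is written for in-app posts suggesting imminent danger, although the investigator is on call for that situation

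*Combined protocol and SAP*

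**What the plan says.** Potential Study Risks (under Risk / Benefit) recognises that people with suicidal ideation may enrol. For a participant who is "in imminent danger to themselves or others", it says that the investigator, a psychologist, "will remain on-call to address all participant related risk concerns for the duration of the study". A numbered list follows, introduced by "Our provisions for clinical management regarding suicide risk in participants include". Its four steps are these:

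1. The moderators' part is given as "Flagging of any suicidal intentions, thoughts, or behaviors disclosed in the GUIDE App to the research team within 24 hours (via GUIDE moderators".
2. Help open to participants themselves is given as "Offering the participants immediate access to mental health resources via the SOS button in the GUIDE app", with the 988 line among them.
3. Review of the flagged message with the investigator "within 12 hours of receipt of the escalation".
4. Contact depends on a judgement: if the investigator "determines that the message is indeed deemed to be indicative of suicidal risk", the step that follows is that "she will contact the participant within 12 hours by phone and/or email".

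The section adds that the investigator will call a local hospital where indicated. It also says that contact details are held partly so that a participant can be reached if clinical risk may be imminent.

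The Procedures section (under Study Procedures) describes the same pathway from the app side. Moderators monitor the small-group chats. They work part-time and hold qualifications in crisis intervention, peer support and critical-incident stress management, among others. Posts about suicide go to the research team by email within 24 hours, under the participant's username. The investigator looks into the matter within 12 hours of receipt and contacts the participant by phone or email.

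**The concern.** The on-call commitment is useful only if the investigator hears of the danger in time to act. For a post in the app, the investigator depends on a moderator passing it on. The protocol gives that step one speed, up to 24 hours by email, whether the post is a passing remark or a statement of immediate intent. A moderator who follows the text to the letter could leave an imminent-danger post until near the end of that window and still comply.

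A second, smaller mismatch sits beside this. The commitment covers danger to others, while the written conditions for passing a post on and for contacting the participant refer only to suicide.

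What is at stake is participant safety, and possibly that of a third party. Randomization, outcomes and analysis are not affected.

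**Working it through.** The plan states no end-to-end time, so there is no figure to reproduce. The check sets the two sections side by side, adds their limits, and looks for any faster staff route elsewhere.

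**Stated limits**

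| Step | Procedures | Potential Study Risks |
|---|---|---|
| Moderator to research team | 24 h, by email | 24 h, route not stated (step 1) |
| Investigator review | 12 h from receipt | 12 h from receipt (step 3) |
| Contact with participant | no clear separate clock | 12 h, start not stated (step 4) |
| Shorter limit if danger looks imminent | none | none |

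**Outer limit from post to contact**

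- If contact falls inside the 12 hours from receipt: 24 + 12 = 36 h.
- If the step 4 clock starts only once the review is finished: 24 + 12 + 12 = 48 h.

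Both totals assume that the 24 hours run from posting. Neither section says so. If they run from the time a moderator first sees the post, both totals lengthen by the unseen interval. The protocol does not bound that interval: the moderators are part-time and no hours of chat coverage are given.

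**Participants concerned.** The Design section gives two arms with immediate access, 50 + 50 = 100 of up to 150 participants. This counts people with app access during the trial period, not people at risk. The documents give no rate of imminent-danger posts or of threats to others, and none is assumed here.

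**Possible faster routes elsewhere**

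- *SOS button (step 2).* Immediate, but the participant must use it, and no alert to staff is described.
- *Hospital contact.* Made by the investigator, so for an in-app post it comes after the same flag. It has no time limit of its own.
- *Contact details.* These let the investigator reach someone once told. They do not speed up the telling.
- *Adverse Event Checklist.* Reviewed at the post-trial meeting (Administration of Surveys and/or Process), too late for a post made during the four weeks.
- *Data and Safety Monitoring.* A general statement that the investigator monitors safety, with no trigger or time.
- *In-app screeners.* The app does not collect the scores, so they send no signal to staff unless the participant posts a result.

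None of these supplies a faster route from moderator to investigator.

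**The case against.** The strongest reply has four parts.

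*The limits are ceilings.* A moderator may escalate at once, and people with crisis-intervention and critical-incident training probably would. This stands as a reason to keep the point small. It does not remove the point, because the text does not ask for speed and fixes email as the route.

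*The list is about suicide by its own heading and is not exhaustive.* This also stands. A reader might infer that the protocol contradicts itself, or count three separate conditions (the Procedures trigger, step 1 and step 4) that each leave out threats to others. The documents do not support either inference. The three conditions are one suicide policy written in two places, under a heading that says so and is introduced with a word that leaves room for more. Suicide is also the risk that Background and Potential Study Risks identify as raised in these groups; neither says the same of harm to others. Taken alone, the missing mention of others is close to a missing detail.

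*Chat is not the only channel.* Staff meet each participant by Zoom at intake and after the trial, and the on-call commitment has real content there. That is correct. The gap concerns only posts made in the app between those meetings.

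*The detail may be elsewhere.* Moderator instructions and attached documents are not visible and may already cover urgent posts. The point is therefore confined to the protocol text. If such instructions exist, aligning the text with them is easier still.

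**Conclusion.** The point holds as a modest safety gap, of minor severity and cheap to close. The only written staff timetable for in-app posts allows 24 hours by email and then 12 hours for review, with a 12-hour contact limit of unstated start. Nothing shorter is written for the imminent-danger case in which the investigator is said to be on call.

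The 36-hour and 48-hour totals are readings of outer limits, conditional on the 24 hours starting at posting. A reader might take them as the delay to expect, or conclude that participants in crisis have nothing sooner. Neither follows: the limits permit earlier action, and the SOS button offers crisis lines immediately. The study is also described as minimal to no risk in Risk / Benefit Assessment, and no event rate is available to size the consequence.

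The harm-to-others wording is secondary. It is worth aligning with the on-call commitment while the text is open.

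**What to change.** **Main change.** In Procedures and in step 1 of Potential Study Risks:

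- Require moderators to alert the on-call investigator as soon as they see a post suggesting imminent danger to self or others, by a direct route such as phone and not by email alone.
- Have the investigator review the post and contact the participant promptly in those cases.
- Keep 24 hours and 12 hours as outer limits for all other posts.

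Because alerts carry only a username, the on-call investigator will need ready access to the username-to-Study-ID list and the contact details already held.

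**Secondary change.** Add harm to others to the Procedures trigger and to steps 1 and 4. The investigator should settle in advance how to respond when a third party is threatened.

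**Cost.** A sentence or two and a phrase in two sections, an on-call number, and the same wording passed to the moderators. Some extra escalations will need review; their number cannot be estimated from the documents. Wider escalation could reduce candour in chats that are anonymous to limit stigma, although posts about suicide are already escalated from them. The consent form may need a matching line on the limits of confidentiality, with the ethics review that entails.

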### **Resources necessary for human research protection**

Describe research staff and justify that the staff are adequate in number and qualifications to conduct the research. Describe how you will ensure that all staff assisting with the research are adequately informed about the protocol and their research related duties. Please allow adequate time for the researchers to conduct and complete the research. Please confirm that there are adequate facilities for the research.

The research team includes the Principal Investigator, [name], a Research Assistant Professor in the Penn Center for Mental Health, University of Pennsylvania and Director of the Digital Mental Health @ Penn Working Group. She will direct all research activities on the proposed project. There will also be a dedicated Clinical Research Coordinator, [name], who has a BA in Psychology and prior research experience. She will be responsible for all organizational tasks of the proposed study, including recruitment and scheduling, as well as many routine administrative tasks and data entry. [name], a Senior Research Assistant, will also assist with administrative tasks. All

research staff completed human subjects training and will undergo training on the study protocol with the PI of the study before contact with any human subject data. The Center for Mental Health, UPenn has adequate facilities for the research. The GUIDE App team will assist the research team with the recruitment of first responders, soldiers and veterans, as advised by our research team. The research team will be responsible for enrollment, app training, intake and post-trial meetings with participants, data collection, analysis, and documentation. The research team will also be responsible for participant compensation to all groups, while the GUIDE team will be responsible for providing additional compensation to the immediate with incentives group.

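### The promised immediate crisis resources sit only in the GUIDE App, so as written they do not reach the waitlist arm in its 4-5 weeks without the app

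*Combined protocol and SAP*

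**What the plan says.** Potential Study Risks recognises that participants with suicidal ideation may join, given the raised risk in all the populations recruited. Separately, it names as a possible harm "experiencing discomfort in talking about their experiences and emotions during the post-trial interview or in filling out the surveys".

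Its provisions come in two parts. The first is general. If a participant is "in imminent danger to themselves or others", the investigator, a psychologist, "will remain on-call to address all participant related risk concerns for the duration of the study". The section also says that the investigator "will contact a local hospital if indicated", and that phone, email and alternate contact details will be held for every participant.

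The second part is a numbered list of four items:

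1. "Flagging of any suicidal intentions, thoughts, or behaviors disclosed in the GUIDE App to the research team within 24 hours", done by the app's moderators.
2. "Offering the participants immediate access to mental health resources via the SOS button in the GUIDE app".
3. Review of the flagged message with the investigator within 12 hours of the escalation.
4. If that message is judged to show suicidal risk, the investigator "will contact the participant within 12 hours by phone and/or email".

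Study Instruments, Administration of Surveys and/or Process, and Procedures each give the list of crisis lines, and each places it in the app. According to the last two sections, the waitlist arm may take up the app at the post-trial meeting, which is booked for 4 to 5 weeks after intake.

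**The concern.** Item 2 is worded as an offer to participants in general, but it works through a feature that one arm does not have while it is being studied. The risk it addresses is described for the whole sample, not for app users.

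What is at stake is practical. A waitlist participant who is in difficulty between intake and the post-trial meeting has, in the visible text, no crisis list in hand. An app-arm participant has one on the phone. The same is normally true of every participant at the baseline survey. Public hotline numbers are ordinary participant protection and can be given without giving the intervention. The estimand, the sample size and the analysis are not affected.

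**Working it through.** There is no plan figure to reproduce. The check sets each stated safeguard against what the waitlist arm has before its post-trial meeting.

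| Safeguard | Where stated | Needs the app? | Waitlist arm before the post-trial meeting |
|---|---|---|---|
| Flag, review and contact for in-app messages (items 1, 3, 4) | Potential Study Risks; Procedures | Yes, starts from an in-app post | Not applicable: this arm has no chat to moderate |
| Crisis list through the SOS button (item 2) | Potential Study Risks; list in Study Instruments, Administration of Surveys, Procedures | Yes | Not available |
| On-call psychologist | Potential Study Risks | No | Available |
| Hospital contact if indicated; contact details held | Potential Study Risks | No | Available |
| Safety monitoring by the investigator | Data and Safety Monitoring | No | Available; no method stated |
| One-on-one Zoom meeting at intake, run by protocol-trained staff | Administration of Surveys; Resources necessary for human research protection | No | Available |
| Zoom meeting and Adverse Event Checklist at the end | Study Instruments; Administration of Surveys | No | At the post-trial meeting itself |

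Only the SOS row is both relevant to the waitlist arm and missing from it.

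**Size.** Inputs: 50 waitlist participants of 150 planned (Design), and 4 to 5 weeks from intake to the post-trial meeting (Administration of Surveys).

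- Share of the sample: 50 / 150 = 33%.
- Time without the SOS list: 50 x 4 = 200 to 50 x 5 = 250 participant-weeks, at full enrolment with no dropout.

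These figures describe coverage. The documents give no event rate, so they say nothing about expected events.

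**Baseline survey.** The stated order is consent, then the baseline survey, then the intake meeting, where app-arm accounts are created. So normally no arm has the SOS button at baseline. The exception is a participant who completes the survey late, during the intake meeting.

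**Response time (minor part).** For an in-app post, Procedures gives 24 h to escalate plus 12 h to investigate and contact: 24 + 12 = 36 h. Potential Study Risks lists review and contact as separate 12-hour steps. Read in sequence, they give 24 + 12 + 12 = 48 h. For a disclosure made to staff by Zoom or email, the visible text states no limit.

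**The case against.** The case on the other side is substantial, and most of it stands.

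- The numbered list is introduced as what the provisions include, so it is not exhaustive. The sentence on the on-call psychologist comes before it and covers every arm and every channel.
- The flag-review-contact chain exists because the app creates an anonymous chat. Its absence from an arm with no chat is not a deficit.
- A reader might infer that the waitlist arm has no suicide-risk safeguard, or that risk there could not come to light. The documents do not support either inference. That arm has two live one-on-one meetings and the checklist. Staff "will undergo training on the study protocol with the PI of the study before contact with any human subject data", and a psychologist is on call.
- A reader might also infer that the surveys themselves raise suicide risk. The protocol names survey discomfort and possible suicidal ideation in separate sentences and does not link them.
- The consent form, which the Consent overview says covers risks, the REDCap survey files, the checklist questions and the intake training protocol could not be seen. Any of them may already carry a crisis list or a handoff rule.

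The answer to what remains is short. None of the visible non-app safeguards puts crisis resources in the participant's hands. The protocol chose to promise immediate access to them, and the channel it names leaves out a third of the sample. The unseen files are a reason to make the fix conditional, not to leave the wording as it is.

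**Conclusion.** The point holds in a limited form. As written, the immediate-access provision does not reach the 50 of 150 planned participants on the waitlist between intake and the post-trial meeting, 4 to 5 weeks, and normally reaches no arm at the baseline survey. The other safeguards that can apply to the waitlist arm do cover it. The missing time limit for disclosures to staff is a smaller drafting matter, since trained staff with an on-call investigator would be expected to pass a disclosure on anyway.

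This rests on the visible text, on full planned enrolment, and on the baseline survey being done before intake as the protocol asks. It does not show that the trial lacks a crisis list everywhere outside the app, because the attachments could not be checked. It is an inexpensive safety improvement worth considering, not a flaw in the design or the analysis.

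**What to change.** Show the crisis-resource list already built into the SOS button at the end of the REDCap baseline and post-trial surveys and in the intake email, for all three arms. If the consent form or the survey files already do this, cite them in Potential Study Risks and add only what is missing.

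As a minor addition, state in the same section that any suicidal disclosure to study staff outside the app (Zoom, email or the Adverse Event Checklist) goes at once to the on-call investigator, with the existing 12 hours as the outer limit for contact.

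The cost is a text block in two surveys and one email, one or two sentences in the protocol, and one point in the staff training already planned. No new data are needed, because contact details are already held. The downside is that giving waitlist participants public hotline numbers could very slightly narrow the contrast with the app arms.
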